7.6 Procedures for Training Interventionists and Monitoring Intervention Fidelity

Training. Practitioners will complete an online training of Ask-Advise-Refer prior to beginning the study intervention. Practitioners will then complete a live training regarding site-specific study procedures. Practitioners will be given quick guides which provide scripts for the intervention and a list of study procedures.

Fidelity. Fidelity will be monitored via the patient after-visit survey which will ask about practitioner intervention behavior as well as whether medication was provided during the patient's visit to the dentist.

8 STUDY SCHEDULE

8.1 Practitioner enrollment

Practitioners enrolled in the National Dental PBRN in the Midwest and Northeast Nodes who express interest in the study and meet eligibility criteria will be invited to participate. Study information and instructions will be provided to interested practitioners by node personnel. After eligibility is determined and practitioners are enrolled, practice training materials will be provided to describe the participant selection procedures, methods for approaching patients and obtaining informed consent, methods for intervention delivery and data collection, and other study procedures for the practitioners and office staff who will help to execute the study. A summary flow chart will provide an overview of all study visits and study procedures/data collection for each visit. The principal node coordinator will conduct training with the NCs. NCs will conduct in-person or remote protocol and electronic data management system training with practitioners and office staff prior to initiating the study. The training ensures that the practitioner and staff understand the study procedures and receive instruction on the consent process, and the electronic data capture system. The NCs will maintain close contact with the practitioners prior to and throughout the study implementation period.

The study schedule will proceed in the following stages on a rolling basis:

- Each Node will enroll practitioners into the study to obtain a total of approximately 25 practitioners;
- Practitioners will complete activities to be deemed research-ready;
- Prior to beginning data collection, practice staff in the NRTS condition will complete assessments about the feasibility and acceptability of the intervention.
- NCs will train research-ready practitioners and their office staff in the appropriate study procedures.
- Practices will screen and enroll eligible patients into the study.
- At the end of site enrollment, practitioners and practice staff will complete feasibility and acceptability assessments again.
- In addition, at the end of site enrollment 10-12 dentists and 10-12 staff involved in the study will complete an interview about acceptability of NRTS and attitudes towards future implementation of NRTS.

An overview of patient study procedures to be completed at each study visit can be found in Appendix A, and the Schedule of Events has been provided in the Appendix at the end of this document.

8.2 Screening/Enrollment/Baseline/study intervention

Visit 1, Day 0

- Practitioner Reviews dental record to determine eligibility criteria
- Practitioner verifies inclusion/exclusion criteria via an electronic screening questionnaire taken by the participant
- Practitioner obtains and documents consent from participant with electronic consent or paper consent. Participants will digitally sign the consent form if offered electronically, and will sign paper consent forms if a paper version is used.
- Participant completes contact information form
- Participant completes baseline survey
- Practitioner provides study intervention

8.3 Follow up Visits¹

Data collection timepoint 2, Day 0 (allowable range 0-14)

- Following visit, administer after visit survey via email, text, or phone.

Data collection timepoint 3, Day 30 (allowable range 28-44)

- Administer 1-month follow-up survey via email, text or phone.
 - Assess adverse events via survey.

Data collection timepoint 4, Day 90 (allowable range 83-104)

- Administer 3-month follow-up survey via email, text or phone.
 - Assess adverse events via survey.

Data collection timepoint 6, Day 180 (allowable range 173-210)

- Administer 6-month follow-up survey via email, text or phone.
 - Assess adverse events via survey.

Data collection timepoint 7, Day 180 (allowable range 174-234)

- Participants who are abstinent will take a CO test

Data collection timepoint 8, Day 180 (allowable range 173-240)

¹ Note: Participants may choose to complete the survey out of the timeframe without prompting from study staff.

- 10-12 patient participants in NRTS condition complete an interview about acceptability of NRTS and attitudes about future implementation of NRTS

9 STUDY PROCEDURES/EVALUATIONS

9.1 Study Procedures/Evaluations

9.1.1 Screening and enrollment (day 0; in dental practice)

- Participants will be enrolled during a routine dental visit at their general practice dental provider's office. Patients who smoke combustible cigarettes will be offered the study.
- Interested participants will complete a screening assessment via REDCap on tablet or via a link texted or emailed to their phone. The self-report eligibility screen includes age, smoking status, smartphone ownership, medical contraindications to NRT (pregnancy, breastfeeding, recent heart attack or stroke), and smoking cessation medication use in the past week (any use of nicotine replacement therapy [patch, gum, inhaler, lozenge, nasal spray], any use of Chantix/varenicline, use of bupropion/zyban/Wellbutrin for the purpose of quitting smoking).
- Finally, interested and eligible participants will complete an electronic written informed consent via REDCap or will complete a paper consent form. If required a HIPAA form will be completed on paper or electronically (depending on the regional IRB rules).

9.1.2 Baseline survey (day 0; in dental practice)

The baseline survey will be administered prior to the intervention. It includes the following measures:

- Contact information
- Demographics (biological sex, gender, ethnicity, race, age)
- Toothbrushing habits
- Smoking history (cigarettes per day, time to first cigarette in the morning, previous quit attempts, past cessation treatment)
- Interest in quitting
- Confidence to quit
- Attitudes about nicotine replacement therapy

9.1.2 Study intervention (day 0; in dental practice)

Practitioners, using a script, will provide the study intervention (see 7.4). They will:

- Ask about smoking status
- Advise those who report smoking to quit
- Offer a referral to the state quitline

- Provide a sample bag containing either nicotine replacement therapy or an electric toothbrush.

9.1.3 After visit survey (Target day 0, in dental practice or remotely)

Following the dental visit, participants will be sent a link via email or text with an after-visit survey. If participants do not respond to the survey within 3 days, they will receive a phone call from Hennepin Healthcare study staff. They will be paid \$20 for after visit survey completion.

The after-visit survey will assess the following:

- the elements of ask-advise-refer as a fidelity check (asked about smoking, advised to quit, asked about interest in quitting, discussed medications, advised to use medication, provided with medication, referred to quit line)
- Demographics (educational attainment, urban/suburban/rural community, zip code, number in household, income, health insurance, dental insurance)
- oral health status
- relationship with dentist
- other non-cigarette tobacco product use
- acceptability of the intervention

9.1.4 1-month follow-up survey (target day 30, conducted remotely)

The one-month follow-up survey will be conducted via email or text. Participants who do not respond will be followed up by phone and/or mail. Participants will be paid \$20 for survey completion.

The one-month follow-up survey will assess the following:

- smoking behavior (smoking each day for the past 7 days, date of last cigarette)
- use of other tobacco products (electronic cigarettes, hookah, cigars, chewing tobacco, snus, pipes, other)
- quit attempts
- use of nicotine patch and lozenge (including sample patches and patches purchased outside of study; use in past 7 days, ever use)
- reasons for nicotine patch/lozenge use
- perceived patch/lozenge effectiveness
- enjoyment of patch/lozenge
- use/purchase of smoking cessation medications,
- use of smoking cessation counseling
- patch/lozenge side effects (nausea, headache, heartburn, mouth soreness, dizziness, dry mouth, sore jaw, excessive salivation, insomnia, hiccups, burning in throat/mouth, skin irritation, skin redness, skin itchiness)

- belief that side effects were caused by patch/lozenge
- perceived oral health status
- frequency of toothbrushing
- type of toothbrush
- interest in stopping smoking
- readiness to quit
- attitudes about nicotine patch, lozenges.

9.1.5 3-month follow-up survey (Target day 90, conducted remotely)

The 3-month follow-up survey will be conducted via email or text. Participants who do not respond will be followed up by phone and/or mail. Participants will be paid \$20 for survey completion.

The 3-month follow-up survey will assess the following:

- smoking behavior (smoking each day for the past 7 days, date of last cigarette)
- use of other tobacco products (electronic cigarettes, hookah, cigars, chewing tobacco, snus, pipes, other)
- quit attempts
- use of nicotine patch and lozenge (including sample patches and patches purchased outside of study; use in past 7 days, ever use)
- reasons for nicotine patch/lozenge use
- perceived patch/lozenge effectiveness
- enjoyment of patch/lozenge
- use/purchase of smoking cessation medications,
- use of smoking cessation counseling
- patch/lozenge side effects (nausea, headache, heartburn, mouth soreness, dizziness, dry mouth, sore jaw, excessive salivation, insomnia, hiccups, burning in throat/mouth, skin irritation, skin redness, skin itchiness)
- belief that side effects were caused by patch/lozenge
- perceived oral health status
- frequency of toothbrushing
- type of toothbrush
- interest in stopping smoking
- readiness to quit
- attitudes about nicotine patch, lozenges.

9.1.5 6-month follow-up survey (Target day 180, conducted remotely)

The 6-month follow-up survey will be conducted via email or text. Participants who do not respond will be followed up by phone and/or mail. Participants will be paid \$20 for survey completion.

The 6-month follow-up survey will assess the following:

- smoking behavior (smoking each day for the past 7 days, date of last cigarette)
- use of other tobacco products (electronic cigarettes, hookah, cigars, chewing tobacco, snus, pipes, other)
- quit attempts
- use of nicotine patch and lozenge (including sample patches and patches purchased outside of study; use in past 7 days, ever use)
- reasons for nicotine patch/lozenge use
- perceived patch/lozenge effectiveness
- enjoyment of patch/lozenge
- use/purchase of smoking cessation medications,
- use of smoking cessation counseling
- patch/lozenge side effects (nausea, headache, heartburn, mouth soreness, dizziness, dry mouth, sore jaw, excessive salivation, insomnia, hiccups, burning in throat/mouth, skin irritation, skin redness, skin itchiness)
- belief that side effects were caused by patch/lozenge
- perceived oral health status
- frequency of toothbrushing
- type of toothbrush
- interest in stopping smoking
- readiness to quit
- attitudes about nicotine patch, lozenges.

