10 ASSESSMENT OF SAFETY

10.1 Specification of Safety Parameters

Safety monitoring for this study will focus on Unanticipated Problems (UPs) involving risks to participants, including unanticipated problems that meet the definition of a serious adverse event. In addition, adverse events (AEs) including SAEs will be recorded, and the PI will monitor these events to grade severity, relationship to the study intervention, and assess whether the nature, severity, or frequency is unexpected. Any time a participant spontaneously reports (calls the study or the practitioner) an AE including SAE or UP, it will be recorded. Practitioners will be trained to direct any participants reporting AEs to Hennepin Healthcare study staff and will alert study staff of any reports of AEs. Adverse events to study medication will be queried at the 1-, 3-, and 6-month follow-up assessments.

Safety events will be recorded and reported into the National Dental PBRN safety event reporting system maintained by the NCC if the events are determined to be both unexpected and related to the study intervention. Study PI [name], will be informed via the safety event system when events are reported.

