10.1.2 Adverse Events

An adverse event is any untoward or unfavorable medical occurrence in a human subject, including any abnormal sign (for example, abnormal physical exam or

laboratory finding), symptom, or disease, temporally associated with the subject's participation in the research, whether or not considered related to the subject's participation in the research.

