10.2 Time Period and Frequency for Event Assessment and Follow-Up

The PI will record all events with start dates occurring any time after informed consent is obtained until 7 (for non-serious AEs) or 30 days (for SAEs) after the last day of study participation. At each study visit, the investigator will inquire about the occurrence of AE/SAEs since the last visit. Events will be followed for outcome information until resolution or stabilization. We also instruct participants to contact study staff via phone if they have problems with the medication

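### The follow-up surveys, as itemised, ask only about patch and lozenge side effects, although Sections 8.3 and 10.2 and Appendix A promise AE/SAE assessment for every patient

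*Protocol*

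**What the plan says.** The protocol describes safety ascertainment in two ways.

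The broad description:
- Section 10.2: "At each study visit, the investigator will inquire about the occurrence of AE/SAEs since the last visit". The same section sets the recording scope: "The PI will record all events with start dates occurring any time after informed consent is obtained", with a closing date 7 days (non-serious AEs) or 30 days (SAEs) after the last day of participation.
- Section 10.1.2 defines an adverse event "whether or not considered related" to taking part in the research.
- Section 8.3 gives the same instruction at days 30, 90 and 180: "Assess adverse events via survey". It is not limited to NRT or to one arm.
- Appendix A has a row for adverse event assessment at 1, 3 and 6 months, separate from the follow-up survey row, in a schedule that covers all patients.
- Section 10.4.2 sends every AE that meets the SAE criteria to the central safety system, with no filter for arm or relatedness.

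The narrow description:
- Section 10.1: "Adverse events to study medication will be queried at the 1-, 3-, and 6-month follow-up assessments". For the rest: "Any time a participant spontaneously reports (calls the study or the practitioner) an AE including SAE or UP, it will be recorded".
- Sections 9.1.4 and 9.1.5 (the latter number heads both the 3-month and the 6-month survey) give identical lists of content. The safety items are "patch/lozenge side effects (nausea, headache, heartburn, mouth soreness, dizziness, dry mouth, sore jaw, excessive salivation, insomnia, hiccups", then throat or mouth burning and three skin symptoms, followed by "belief that side effects were caused by patch/lozenge".

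**The concern.** After day 0 the planned follow-up is remote. Section 6.3 has patients complete the surveys online, and staff telephone those who have not answered by the fifth day. A patient who answers the link promptly has no scheduled conversation in which the enquiry of Section 10.2 could take place. The survey must therefore carry it, and Section 8.3 says that it does.

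If the surveys are built from the lists in Sections 9.1.4 and 9.1.5, a patient admitted to hospital in month 2 meets no question that would bring this out. The study would then miss events that its own Sections 10.2 and 10.4.2 oblige it to record and report, and the monthly safety review by the principal investigator (Section 11) would rest on incomplete data. The primary abstinence analysis is not affected.

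**Working it through.** The point depends on no power, alpha or event figure, so the check is a comparison of text and a count of items.

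**1. Safety items in the stated survey content.** The quoted run names 10 symptoms (nausea to hiccups). The rest of the list adds 4: throat or mouth burning, and skin irritation, redness and itchiness. 10 + 4 = 14, all presented as patch or lozenge effects, and the same in all three surveys. One further item asks about attribution to patch or lozenge. Open questions on health problems: 0. Items on hospital stay, emergency care or any other SAE consequence: 0. Items on toothbrush harm: 0. The after-visit survey in Section 9.1.3 lists no adverse event item.

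**2. Three events traced through both descriptions.**

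| Event | Sections 10.2, 8.3, Appendix A | Sections 9.1.4/9.1.5 and 10.1 |
|---|---|---|
| Hospital admission, either arm | Asked about and recorded; reported under 10.4.2 | No item; surfaces if volunteered |
| Effect outside the list, such as the vivid dreams or stomachache that Section 3.3.1 itself anticipates | Asked about and recorded | No item |
| Any event in a toothbrush-arm patient who uses no patch or lozenge | Asked about and recorded | Side-effect items do not apply |

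**3. Numbers exposed.** The first row concerns all patients: about 50 practices × 24 = 1200. The third concerns part of the toothbrush arm: about 25 practices × 24 = 600, less those who obtain NRT themselves. If a share *u* does so, the number is 600 × (1 − *u*). The protocol gives no *u* for this arm. As an assumption, take *u* from 0 to 0.30; the upper value borrows the background figure in Section 3.1 that fewer than 30 percent of smokers use medication in a quit attempt. The range is then 600 × 1 = 600 down to 600 × 0.70 = 420.

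**4. Can the two descriptions be read as one?** Section 10.1 could be read as covering only part of what is asked. But Section 8.3 places the adverse event assessment inside the survey, and the survey content is given symptom by symptom. No general question is described in Sections 8 to 10.

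**The case against.** The lists in Sections 9.1.4 and 9.1.5 are summaries of topics, not the questionnaires. Section 10.3 mentions a case report form for each event, and neither it nor the survey instruments are in the document. A general question may exist. This limits the claim to the content as stated, but the conflict on the page remains.

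Other reporting routes exist. Sections 3.3.1 and 6.5.2 tell patients to contact the study team about an SAE, Section 10.2 tells them to call about medication problems, and Section 10.1 has practitioners pass on reports. For a two-week supply of over-the-counter products or a toothbrush, targeted questions plus spontaneous reports would be a defensible choice. But the protocol does not state that choice; it commits itself to more.

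A reader might infer several stronger points that the documents do not support:
- *Every toothbrush-arm event is found only by spontaneous report.* Section 8.3 and Appendix A schedule an assessment for all patients, and the survey covers patches obtained outside the study, so toothbrush-arm patients who use NRT would meet the side-effect items. Everyone is also asked about oral health and toothbrushing, which could pick up some toothbrush harm indirectly.
- *The arms get different questions.* One survey is described, with no rule by arm.
- *A comparator rate is missing for judging excess events.* Section 10.3.2 judges expectedness against known risk information for the intervention, and no between-arm comparison of AEs is planned.
- *The enquiry is promised at every contact.* Section 10.2 speaks of study visits. Treating the surveys as visits is reasonable because Section 8.3 lists them under follow-up visits, but it is an inference.
- *The list is deficient because none of its 14 symptoms is an SAE criterion.* Those criteria are mostly consequences such as death or hospitalisation, so no symptom list would contain them. The gap is the absence of any question on such consequences.

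**Conclusion.** The concern holds as an internal contradiction with a practical consequence. Sections 8.3 and 10.2 and Appendix A promise AE/SAE assessment for all patients; the survey content in Sections 9.1.4 and 9.1.5 and the scope in Section 10.1 provide for patch and lozenge effects only. With that content, SAEs in either arm (about 1200 patients), unlisted events, and events in toothbrush-arm patients without NRT (at most about 600) depend mainly on the patient or practitioner coming forward.

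This rests on three assumptions: that the lists reflect the instruments, that no unshown form puts a general question to patients, and that the surveys are the visits Section 10.2 has in mind. It should be corrected, though the expected product risk is low. It does not show that events have been or will be missed at any particular rate.

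**What to change.** Reconcile Sections 8.3, 9.1.4, 9.1.5, 10.1 and 10.2 and Appendix A so that they state one scope for the scheduled adverse event query. To meet the scope that Section 10.2 already sets, add two items to the 1-, 3- and 6-month surveys, worded identically in both arms:
- an open question on any new or worse health problem since the last survey;
- a question on any hospital stay or emergency visit since the last survey.

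Keep the patch and lozenge list as an additional item, and amend the sentence in Section 10.1 to match. If the questionnaires already contain such items, listing them in Sections 9.1.4 and 9.1.5 and correcting Section 10.1 is enough.

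The cost is two items in each of three surveys and staff time to triage events, many of which will be unrelated. Treatment, schedule and primary outcome stay as they are.

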9.1.6 CO test (target day: within one week of 6-month follow up survey)

Participants who report being abstinent for the past 7 days on the 6-month follow-up survey will be sent, via overnight mail, a portable CO monitor (iCOquit, Bedfont Scientific) with instructions for use. Participants will be instructed to take the CO test within 24 hours of receipt. If they do not take the test within 24 hours, the study will provide email, text, or phone reminders daily for 14 days. Patient participants will download the iCOquit app onto their cellphones. The study will provide a username and password for the app. The participant will then follow the instructions on the app to take a CO test. Hennepin Healthcare study staff will log into the app (with the pre-specified username and password given to the participant) to get the test result. Thus, all the data from the iCOquit is deidentified (a username and passcode provided by the study, and the participant's test result). They will be instructed to delete the app once CO data is received. Participants will be paid \$50 for a completed CO test.

9.1.7 Patient interview (target day: within one month of 6-month follow-up survey)

10-12 patients in the NRTS condition will be selected to participate in a 60-minute interview by study staff at Northwestern University about the feasibility and acceptability of NRTS. Participants will be paid \$50 to participate in the interview.

9.1.8 Clinic Staff Baseline Surveys (Prior to staff training in study procedures)

Prior to receiving training, all clinic staff at sites assigned to the NRTS condition who will be involved in the conduct of the FreSH trial will complete baseline surveys. Surveys to be administered include:

- Organizational Readiness for Change (to be completed by the person at the clinic who will perform the study intervention)
- Feasibility of intervention measure
- Acceptability of intervention measure
- Appropriateness of intervention measure

